### 8.2.5.2 Statistical Methods for Safety Analyses

Safety parameters will be compared between V920 and placebo control. Fisher's exact or Chi-square test will be used to compare the frequency of local and systemic reactions between treatment groups as specified in the SAP.

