#### 4.3.1.3 Reactions to V920

Detailed safety data collected in the Phase 2 and 3 studies to date have demonstrated V920 to be generally well-tolerated when administered to healthy, non-pregnant, adults. Injection site reactions following vaccination are generally mild to moderate and self-limited. Thereafter, there is a predictable period of early reactogenicity, including fever and a flu-like syndrome and resolves with 7 days. During this time, transient decreases in white blood cells and platelets

have also been observed but bleeding or increased risk of infection has not been reported. The early reactogenicity is likely to be a result of viremia with the vaccine virus which resolves within 2 weeks. Vaccine virus has been found in saliva, urine, and skin-vesicles in vaccines. Person-to-person transmission has not been documented, however transmission through shedding and close personal contact is accepted as a theoretical possibility. Joint pain (arthralgia) is part of the early flu-like syndrome in the first week after vaccination in up to 44% of vaccines. In a small proportion of subjects (<5%), joint swelling (arthritis) may develop in the 2nd to 3rd week after vaccination. The arthritis is thought to be virally-mediated, and while the majority of arthralgia and arthritis events resolved spontaneously, recurrent or persistent arthralgia and arthritis have also been reported. The safety profile reported from the Ebola-epidemic region has been similar to that observed outside the region.

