### 8.2.2 Objectives/Hypotheses

(1) Objective: Evaluate the safety and tolerability of V920 in HIV-infected adults and adolescents.

(2) Objective: Evaluate the immunogenicity of V920 via ZEBOV-specific antibody responses induced by V920 at D28 in HIV-infected adults and adolescents.

Primary Hypotheses:

- 1) The geometric mean titer (GMT) of GP-ELISA in V920 vaccinated HIV-infected adults and adolescents will be superior to the GMT of the GP-ELISA in placebo vaccinated HIV-infected adults at Day 28 in Cohorts 1-5 combined.

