### 8.2.5 Statistical Methods

#### 8.2.5.1 Statistical Methods for Immunogenicity Analyses

Immunogenicity summaries will include: means and 95% CIs of the Geometric Mean Titers (GMT) and Geometric Mean Fold Increase from baseline (GMFI) of ZEBOV-specific antibody responses at baseline and Day 28, Day 84 (Cohort 5 only), Day 180, and Day 365.

Immunogenicity summaries will include: counts, percentages, and 95% CIs of subjects who achieve seroconversion (e.g. 4-fold increase) for ZEBOV-specific antibody responses at baseline and Day 28, Day 84 (Cohort 5 only), Day 180, and Day 365.

Immunogenicity summaries will include: counts, percentages, and 95% CIs of subjects who achieve seroprotection for ZEBOV-specific antibody responses at baseline and Day 28, Day 84 (Cohort 5 only), Day 180, and Day 365 based on correlate of protection thresholds, if found. Fisher's exact (primary) or Chi-square test (secondary if proportion size warrants) will be used to compare the frequency of ZEBOV-specific antibody responses and Student's t (primary) or Wilcoxon rank-sum test (secondary if not normally distributed) will be used to compare ZEBOV-specific GMT ZEBOV-specific antibody between treatment groups. All hypotheses will be evaluated using two-sided tests at  $\alpha = 0.05$ . Superiority of immune response will be defined as a statistically significant difference.

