#### Vaccine reactogenicity

Counts and percentages of solicited local and systemic reaction frequency and severity among study cohorts (various CD4 counts and ages) will be summarized.

Adverse events will be classified by Medical Dictionary for Regulatory Activities (MedDRA®) system organ class and preferred term, severity, seriousness, investigator causality assessment, and time since vaccination.

Safety listings will display all safety events, including a separate display of solicited post-treatment reactions, and all other AEs.

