### 8.2.7 Sample Size and Power Calculations

For immunogenicity assessment, there is 80% power to detect a Geometric Mean Ratio (GMR) of 1.6 (V920 GP-ELISA GMT of 58 EU/mL vs. Placebo GP-ELISA GMT of 36 EU/mL, the lower limit of quantification [LLOQ]) and 90% power to detect a GMR of 1.7 (V920 GP-ELISA GMT of 62 EU/mL) if comparing all five cohorts (N=200 V920 vs. N=50 Placebo) combined. This power analysis assumes a 10% dropout, a standard deviation of 1 on the log scale, and a 2-sided 5%.

There is 80% power to detect a GMR of 2.9 (V920 GP-ELISA GMT of 105 EU/mL) and 90% power to detect a GMR of 3.4 (V920 GP-ELISA GMT of 124 EU/mL) if comparing each cohort independently (N=40 V920 vs. N=10 Placebo). This power analysis assumes a 10% dropout, a standard deviation of 1 on the log scale, and a 2-sided 5%.

For safety assessment, there is 80% power to detect a 12% difference in event rates that occur with a frequency of 1% in the control group if comparing four cohorts (N=200 V920 vs. N=50 Placebo) combined and a 46% difference if comparing each cohort independently (N=40 V920 vs. N=10 Placebo).

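### Safety, the first primary objective, is compared between arms only by a significance test of reactions; no risk difference, confidence interval or upper bound is planned for any safety endpoint

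*Combined protocol and SAP*

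**What the plan says.** Section 8.2.2 lists as the first objective: "Evaluate the safety and tolerability of V920 in HIV-infected adults and adolescents". Section 4.2.3.2 makes arthritis, arthralgia, rash and vesicular lesions over 42 days primary safety endpoints, along with other solicited reactions, unsolicited events, laboratory abnormalities and vaccine-related SAEs.

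Section 8.2.5.2 commits to a comparison: "Safety parameters will be compared between V920 and placebo control". The only between-group method it then names is: "Fisher's exact or Chi-square test will be used to compare the frequency of local and systemic reactions between treatment groups". It adds that this will be as the SAP specifies, but Section 8.0 is itself the SAP and gives no more. Section 8.1 says the same.

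The other planned safety outputs are descriptive: "Counts and percentages of solicited local and systemic reaction frequency and severity among study cohorts", MedDRA classification, listings, and means with standard deviations for vital signs and laboratory values.

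For immunogenicity proportions, Section 8.2.5.1 plans "counts, percentages, and 95% CIs of subjects who achieve seroconversion", and it likewise attaches 95% CIs to GMTs, fold increases and seroprotection.

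Section 8.2.7 claims "80% power to detect a 12% difference in event rates that occur with a frequency of 1% in the control group" for 200 versus 50. Section 4.3.1.3 says of arthritis after V920: "In a small proportion of subjects (<5%), joint swelling (arthritis) may develop".

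**The concern.** A test answers whether a difference has been shown. A safety objective also needs to know how large an excess the data leave possible. With 50 placebo recipients, or 10 in a single cohort, a test of an uncommon event will usually be non-significant whether or not the vaccine causes it. If the p-value is the only comparative figure, the reader learns almost nothing about that event from the comparison. An interval from the same counts would show what excess has been ruled out.

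The plan already uses intervals for immunogenicity, so safety gets the weaker reporting although it is the first primary objective. Unsolicited events, SAEs and laboratory abnormalities have no between-group method named at all.

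**Working it through.** **Inputs.** Pooled 200 V920 and 50 placebo; per cohort 40 and 10 (Section 8.2.7). Two-sided 5% (Section 8.2.5.1; assumed to apply to safety). Arthritis below 5%, with 5% taken as the ceiling, and arthralgia up to 44% (Section 4.3.1.3). The documents give no placebo rates: 0% to 1% is assumed for arthritis and 20% for arthralgia.

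**The plan's own pooled figure (13% versus 1%).** Normal approximation:
- average rate = (200×0.13 + 50×0.01)/250 = 0.106
- SE under no difference = √[0.106×0.894×(1/200 + 1/50)] = 0.0487
- SE under the alternative = √[0.13×0.87/200 + 0.01×0.99/50] = 0.0276
- z = (0.12 − 1.96×0.0487)/0.0276 ≈ 0.89, so power is about 81%

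This reproduces the stated 80%. Exact enumeration of Fisher's test gives 83%. The per-cohort figure of 46 points does not come from the same formula (which gives about 93% power), but nothing below depends on it.

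**Events needed.** With 0/50 on placebo, Fisher's two-sided p is 0.079 at 14/200 and 0.047 at 15/200. The threshold is therefore 15/200 (7.5%), while a 5% rate gives 10 expected cases. In one cohort with 0/10 on placebo, the threshold is 13/40 (32.5%).

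**Power for an uncommon harm.** Power is the sum of the binomial probabilities of all outcomes with Fisher p ≤ 0.05. When the placebo rate is zero this is P(X ≥ 15) for X ~ Bin(200, 0.05) = 7.8%.

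| Arms | V920 vs placebo rate | Power | Non-significant |
|---|---|---|---|
| 200 vs 50 | 5% vs 0% | 7.8% | 92.2% |
| 200 vs 50 | 5% vs 0.5% | 6.1% | 93.9% |
| 200 vs 50 | 5% vs 1% | 4.7% | 95.3% |
| 200 vs 50 | 4% vs 0% | 1.5% | 98.5% |
| 200 vs 50 | 3% vs 0% | 0.1% | 99.9% |
| 180 vs 45 (10% loss assumed) | 5% vs 0% | 3.7% | 96.3% |
| 40 vs 10 | 5% vs 0% to 1% | about 0% | about 100% |

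**Power for a common reaction.** Arthralgia at 44% versus 20% has 89% power at 200 versus 50, and 21% at 40 versus 10.

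**What an interval adds.** Take 10/200 versus 0/50, where Fisher p = 0.22. The Wilson limits are 2.74% to 8.96% for V920 and 0% to 7.13% for placebo. The Newcombe 95% CI for the 5.0-point difference is then:
- lower: 5.0 − √[(5.0 − 2.74)² + 7.13²] = −2.5 points
- upper: 5.0 + √[(8.96 − 5.0)² + 0²] = +9.0 points

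The p-value gives no hint that a 9-point excess remains compatible with the data. The exact interval for the V920 arm alone is 2.4% to 9.0%.

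For zero events the exact upper limit is 1 − 0.025^(1/n): 1.8% for 0/200 and 8.8% for 0/40.

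**The case against.** The strongest reply has four parts.

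1. **Safety here is descriptive.** Both primary hypotheses in Section 3.1 concern GP-ELISA titres. There is no safety hypothesis or margin. Cohort progression and halting rest on DSMB review and the event-based rules of Appendix 3, not on p-values. A reader might infer that the plan treats a non-significant test as evidence of safety; the documents do not say so. This stands, and it is why the point concerns reporting and not a faulty decision rule.

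2. **The output is not empty.** A reader might infer that nothing will show how much harm is possible. Counts, percentages, severity and listings are planned, and with known denominators anyone could compute an interval. This also stands. What is missing is a commitment to report one and to draw conclusions from it.

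3. **The high miss rate is selective.** A reader might infer that known V920 harms in general will be missed more than 90% of the time. They will not: the pooled test has about 89% power for arthralgia under the assumed 20% placebo rate. The figure belongs to uncommon events only.

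4. **The test may not cover arthritis.** Section 8.2.5.2 assigns it to local and systemic reactions, and Section 4.2.3.2 lists arthritis separately from the 14-day solicited reactions. The arthritis calculation is therefore conditional on the test being applied. If it is not, arthritis has no between-group method, which does not help the plan.

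Section 8.2.7 also discloses the 12-point and 46-point detectable differences openly. That tells the reader the test is insensitive; it does not supply an estimate.

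**Conclusion.** The concern holds in a limited form. For its first primary objective, the plan names one between-group method, a significance test of local and systemic reactions, and no interval or bound for any safety endpoint. At the 5% ceiling for arthritis, that test is non-significant 92% to 95% of the time at 200 versus 50, and more often at lower true rates or with dropout.

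This rests on an assumed placebo rate of 0% to 1%, on the two-sided 5% level applying to safety, on the test being applied to arthritis, and on a V920 rate that Section 4.3.1.3 reports for healthy adults. It does not extend to common reactions in the pooled comparison. No data, sample size or stopping decision is affected; what changes is what the trial can conclude about excess harm.

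**What to change.** In Sections 8.1 and 8.2.5.2, make these the main safety output for each primary safety endpoint in Section 4.2.3.2, pooled and by cohort:
- the percentage in each arm with an exact (Clopper-Pearson) 95% CI;
- the V920-minus-placebo risk difference with a 95% CI, by Newcombe or Miettinen-Nurminen, chosen in advance;
- the exact upper limit where an arm has no events.

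Keep the Fisher or Chi-square p-values as descriptive. Add a sentence that a non-significant test will not be read as absence of a difference, and that conclusions will rest on the interval.

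The order of precedence should be explicit, because test and interval can disagree near the boundary. For 15/200 versus 0/50, Fisher p is 0.047, yet the Newcombe lower limit is 7.5 − √[(7.5 − 4.60)² + 7.13²] = −0.2 points.

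The cost is SAP wording and a few table columns, with no new data or participants. The downside is that the intervals will be wide, above all by cohort, and will look less reassuring than a list of non-significant p-values: 2/40 versus 0/10 gives −23.0 to +16.5 points by Newcombe.

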### 3.0 OBJECTIVE(S) & HYPOTHESES

#### 3.1 Primary Objective(s) & Hypotheses

- (1) **Objective:** Evaluate the safety and tolerability of V920 in HIV-infected adults and adolescents.
- (2) **Objective:** Evaluate the immunogenicity of V920 via ZEBOV- specific antibody responses induced by V920 in HIV-infected adults and adolescents.

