#### **7.2.5 Evaluating Adverse Events**

An investigator who is a qualified physician will evaluate all adverse events with respect to the elements outlined in Table 4. The investigator's assessment of causality is required for each adverse event. Refer to Table 4 for instructions in evaluating adverse events.

Table4: Evaluating Adverse Events

Maximum Intensity	Mild	awareness of sign or symptom, but easily tolerated (for pediatric trials, awareness of symptom, but easily tolerated)
	Moderate	discomfort enough to cause interference with usual activity (for pediatric trials, definitely acting like something is wrong)
	Severe	incapacitating with inability to work or do usual activity (for pediatric trials, extremely distressed or unable to do usual activities) Injection site redness or swelling from the day of vaccination (D0) through Day 14 post-vaccination will be evaluated by maximum size.
Seriousness	A serious adverse event (AE) is any adverse event occurring at any dose that:	
	†Results in death; or	
	†Is life threatening; or places the subject, in the view of the investigator, at immediate risk of death from the event as it occurred [Note: This does not include an adverse event that, had it occurred in a more severe form, might have caused death.]; or	
	†Results in a persistent or significant disability/incapacity (substantial disruption of one's ability to conduct normal life functions); or	
	†Results in or prolongs an existing inpatient hospitalization (hospitalization is defined as an inpatient admission, regardless of length of stay, even if the hospitalization is a precautionary measure for continued observation. (Note: Hospitalization for an elective procedure to treat a pre-existing condition that has not worsened is not a serious adverse event. A pre-existing condition is a clinical condition that is diagnosed prior to the use of study product and is documented in the patient's medical history.); or	
	†Is a congenital anomaly/birth defect (in offspring of subject taking the product regardless of time to diagnosis); or	
	Is a cancer (although not serious per ICH definition, is reportable to the Sponsor within 24 hours to meet certain local requirements; or	

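### Section 8.2.5.2 tests only how often reactions occur, so a V920-versus-placebo shift from mild to moderate or severe reactions would not be tested

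*Combined protocol and SAP*

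**What the plan says.** Section 8.2.5.2 opens with a general commitment: "Safety parameters will be compared between V920 and placebo control". The only method it then names for reactogenicity is Fisher's exact or chi-square, which "will be used to compare the frequency of local and systemic reactions between treatment groups as specified in the SAP". The summary table in Section 8.1 repeats it.

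Severity appears in two places under the Vaccine reactogenicity subheading. Solicited reactions are described: "Counts and percentages of solicited local and systemic reaction frequency and severity among study cohorts (various CD4 counts and ages) will be summarized". Adverse events are classified by "system organ class and preferred term, severity, seriousness, investigator causality assessment, and time since vaccination". Neither sentence sets severity out by treatment arm or names a test of it.

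Severity is collected. Under Section 7.2.5 a qualified physician "will evaluate all adverse events with respect to the elements outlined in Table 4", and Table 4 grades maximum intensity as mild, moderate or severe. The exception is injection-site redness and swelling, which are evaluated by maximum size through Day 14.

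The first primary objective (Section 3.1) is: "Evaluate the safety and tolerability of V920 in HIV-infected adults and adolescents". Section 4.2.3.2 makes each solicited local and systemic event a primary safety endpoint. Section 4.3.1.3 itself describes the vaccine by grade: "Injection site reactions following vaccination are generally mild to moderate and self-limited".

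**The concern.** Tolerability depends on how bad reactions are as well as how many subjects have one. Section 4.3.1.1 expects pain, swelling or redness with either V920 or placebo, so some background of mild reactions is likely in both arms. Reaction versus no reaction then counts mild soreness after saline the same as an incapacitating symptom after vaccine. If V920 mainly moved reactors from mild to moderate or severe, the two arms could have equal reaction frequencies. The only named test would find nothing, and no planned table would be bound to show the difference by arm. In a live-vaccine trial in people with HIV, that is one of the questions primary objective 1 should answer. Without a stated cut, the severity contrast could also be chosen after unblinding.

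**Working it through.** **Plan's own safety figure.** Section 8.2.7 states 80% power for a 12-point difference with 1% in control, 200 versus 50. The two-sided 5% level is stated there for immunogenicity and assumed here for safety.

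- Pooled rate: (50 × 0.01 + 200 × 0.13) / 250 = 0.106.
- SE under no difference: √[0.106 × 0.894 × (1/50 + 1/200)] = 0.0487.
- SE under the alternative: √[0.01 × 0.99/50 + 0.13 × 0.87/200] = 0.0276.
- Power: Φ[(0.12 − 1.96 × 0.0487) / 0.0276] = Φ(0.89) = 81%.

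The figure reproduces. It concerns event rates; no power statement concerns severity.

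**Assumptions for the severity check.** The documents give no severity distribution by arm, so the ones below are assumed, written as none/mild/moderate/severe in percent. Sample sizes are 200 V920 and 50 placebo, two-sided 5%. Fisher power is by exact enumeration of the two binomials. The rank test is Wilcoxon with tie correction, simulated with at least 40,000 trials per scenario.

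| Scenario | V920 | Placebo | Fisher, any reaction | Wilcoxon on grade | Fisher, moderate-or-severe |
|---|---|---|---|---|---|
| Pure severity shift, 44% react | 56/14/20/10 | 56/33/9/2 | 4% | 16% | 82% |
| Pure severity shift, 30% react | 70/10/14/6 | 70/22/7/1 | 4% | 6% | 52% |
| Pure severity shift, 50% react | 50/15/25/10 | 50/35/13/2 | 4% | 22% | 81% |
| Both rise | 65/18/12/5 | 80/15/4/1 | 52% | 63% | 60% |
| Both rise | 55/22/16/7 | 70/22/7/1 | 44% | 66% | 71% |
| Both rise | 40/25/25/10 | 50/35/13/2 | 22% | 63% | 81% |
| More reactions, same severity mix | 55/27/13.5/4.5 | 70/18/9/3 | 44% | 46% | 14% |
| Only mild reactions rise | 60/34/5/1 | 80/14/5/1 | 76% | 71% | 3% |
| No difference | 80/14/5/1 | 80/14/5/1 | 4% | 5% | 3% |

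Chi-square, which the plan also allows, rejects about 5% in the pure shifts, so the choice between the two named tests does not matter there.

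**The first row in counts.** Any reaction: 0.44 × 200 = 88 versus 0.44 × 50 = 22, identical proportions and p = 1. Moderate-or-severe: 0.30 × 200 = 60 versus 0.11 × 50 = 5.5. With 60/200 against 6/50, Fisher gives p = 0.011. At the assumed rates the risk difference is 30 − 11 = 19 points, with 95% half-width 1.96 × √(0.30 × 0.70/200 + 0.11 × 0.89/50) = 10.7 points, or about 8 to 30.

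**Reading the table.**
- In a pure severity shift, the any-reaction test rejects no more often than chance, and the rank test does little better (6% to 22%). Moderate-or-severe recovers 52% to 82%.
- When frequency and severity both rise, the rank test gains 63 − 52 = 11 to 63 − 22 = 41 points over any-reaction Fisher.
- When only frequency rises, any-reaction is the right contrast and moderate-or-severe is weak. Neither binary contrast replaces the other.

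**Single cohort.** At 40 versus 10, moderate-or-severe Fisher has 14% power for 30% versus 11%. The same size applies to reactions after dose 2, since only Cohort 5 receives one.

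**The case against.** **Severity is not ignored.** Solicited severity is summarised, adverse events are classified by it, and the opening sentence of 8.2.5.2 could be read to cover it. The documents never say yes/no; that is the natural reading of frequency. All this stands, and it rules out saying that severity is discarded. It does not fill the gap. The opening sentence names no severity measure or method. The pointer to the SAP leads nowhere further, because Section 8 is itself titled the Statistical Analysis Plan and gives no more detail.

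**A reader might infer that dichotomising loses power in general, and that an ordinal test should replace it.** The calculations do not support that. With the same severity mix in both arms, the rank test gives 46% against 44% for Fisher and 49% for chi-square. If only mild reactions rise, it loses about 5 points to Fisher. In the pure severity shift it is nearly blind. Its large gains depend on assuming that frequency and severity rise together.

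**Little hangs on it formally.** Both primary hypotheses (Section 3.1) concern GP-ELISA titres, safety has no hypothesis or threshold, and Section 8.2.6 makes no multiplicity adjustment. A severity difference would be visible in a table by arm without a p-value. This stands, and it limits the point to an improvement. But the plan does not commit to that table.

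**Not every reaction has three grades.** Correct: Table 4 evaluates redness and swelling by maximum size and gives no conversion to grades, so the moderate-or-severe cut does not apply to them as written.

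**Conclusion.** The gap is real and narrow. The plan names a between-arm test of reaction frequency only, and nothing in it commits to comparing severity between V920 and placebo. Under the assumed distributions at 200 versus 50, a pure shift to moderate-or-severe reactions (30% versus 11%) is rejected about 4% of the time by the named test and about 82% by the same test applied to moderate-or-severe reactions. With a smaller shift (20% versus 8%) the second figure is 52%.

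These sizes rest wholly on assumed distributions and on all 250 subjects contributing. The absence of a severity comparison does not depend on them. The point concerns the pooled analysis: comparisons at 40 versus 10 stay underpowered whichever test is used. It does not show that the existing test is wrong or generally inefficient, and it touches no confirmatory hypothesis. It is a cheap improvement.

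**What to change.** In Section 8.2.5.2, for each solicited reaction after each dose:

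1. Tabulate each subject's maximum severity (none, mild, moderate, severe) by arm as well as by cohort.
2. Keep the any-reaction test. Beside it, compare moderate-or-severe reactions between V920 and placebo in the pooled cohorts with Fisher's exact test, and report the risk difference with its 95% CI. After dose 2 the data come from Cohort 5 alone, so rely there on the table and interval.
3. Compare redness and swelling on maximum size, or on size categories stated before unblinding.
4. Optionally add an ordinal test (Wilcoxon, or a CMH mean-score test stratified by the randomisation strata) as a supplement.
5. Label the added p-values descriptive.

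The cost is a few sentences and some tables from data already collected. The downside is a few more unadjusted p-values in a largely descriptive safety analysis.
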